# 6.5.3 Rescue Medications and Supportive Care

# 6.5.3.1 mRNA-5671/V941 Supportive Care Guidelines

Participants should receive appropriate supportive care measures for adverse experiences potentially associated with mRNA-5671/V941 administration as deemed necessary by the treating investigator including, but not limited to, the item(s) outlined below.

Management of Cytokine Release Syndrome (CRS): Cytokine release syndrome is defined in CTCAE v4 as a disorder characterized by nausea, headache, tachycardia, hypotension, rash, and shortness of breath. CRS occurs when lymphocytes (B cells, T cells, and/or natural killer cells) and/or myeloid cells (macrophages, dendritic cells, and monocytes) become activated and release inflammatory cytokines [Lee, D. W., et al 2014]. In addition to the symptomatology defined under CTCAE, CRS may present with fever, chills, myalgias, and malaise [Lee, D. W., et al 2014]. Table 4 shows treatment guidelines for participants who experience CRS.

24-MAR-2022

V941-001-08 FINAL PROTOCOL

Table 4 Cytokine Release Syndrome Treatment Guidelines

NCI CTCAE Grade	Treatment	Premedication at subsequent dosing
Grade 1 Mild reaction: Therapy interruption not indicated. Intervention not indicated.	Increase monitoring of vital signs and oxygen saturation, as medically indicated, until the participant is deemed medically stable in the opinion of the Investigator	None
Grade 2 Therapy interruption indicated but responds promptly to symptomatic treatment (eg, NSAIDS, narcotics, IV fluids). Prophylactic medications indicated for ≤ 24 hours	Increase monitoring of vital signs and oxygen saturation, as medically indicated, until the participant is deemed medically stable in the opinion of the Investigator Additional appropriate medical therapy may include, but is not limited to:  IV fluids  NSAIDS  Acetaminophen  Narcotics  Oxygen  Perform fever work-up to exclude infectious etiologies; treat neutropenia if present	Participant may be premedicated 1.5 hours (± 30 minutes) prior to mRNA-5671/V941 administration with acetaminophen 500 to 1000 mg PO (or equivalent dose of antipyretic)
Grade 3 Prolonged (eg, not rapidly responsive to symptomatic medication); recurrence of symptoms following initial improvement; hospitalization indicated for clinical sequelae (eg, renal impairment, pulmonary infiltrates)	Additional appropriate medical therapy may include, but is not limited to:  IV fluids  NSAIDS  Acetaminophen  Narcotics  Oxygen  Pressors  Corticosteroids  Anti-IL6 (eg, tocilizumab)  Empiric antibiotics  Participants with ≥ Grade 3 CRS need to be monitored very closely, likely in an intensive care setting	For Grade 3 CRS, discuss with Sponsor prior to restart of mRNA-5671/V941 treatment.  Participant may be premedicated 1.5 hours (± 30 minutes) prior to mRNA-5671/V941 administration with acetaminophen 500 to 1000 mg PO (or equivalent dose of antipyretic)
Grade 4 Life-threatening consequences; pressor or ventilatory support indicated	Additional appropriate medical therapy may include, but is not limited to:  IV fluids  NSAIDS  Acetaminophen  Narcotics  Oxygen  Pressors  Corticosteroids  Anti-IL6 (eg, tocilizumab)  Empiric antibiotics  Participants with ≥ Grade 3 CRS need to be monitored very closely, likely in an intensive care setting	Permanently discontinue mRNA-5671/V941 in participants who develop Grade 4 CRS

## 6.5.3.2 Pembrolizumab Supportive Care Guidelines

Participants should receive appropriate supportive care measures as deemed necessary by the treating investigator. Suggested supportive care measures for the management of AEs with potential immunologic etiology are outlined along with the dose modification guidelines in Section 6.6, Table 5. Where appropriate, these guidelines include the use of oral or IV treatment with corticosteroids, as well as additional anti-inflammatory agents if symptoms do not improve with administration of corticosteroids. Note that several courses of steroid tapering may be necessary as symptoms may worsen when the steroid dose is decreased. For each disorder, attempts should be made to rule out other causes such as metastatic disease or bacterial or viral infection, which might require additional supportive care. The treatment guidelines are intended to be applied when the investigator determines the events to be related to pembrolizumab.

Note: If after the evaluation of the event, it is determined not to be related to pembrolizumab, the investigator does not need to follow the treatment guidance. Refer to Table 5 in Section 6.6 for guidelines regarding dose modification and supportive care.

It may be necessary to perform conditional procedures such as bronchoscopy, endoscopy, or skin photography as part of evaluation of the event.

## **6.6** Dose Modification (Escalation/Titration/Other)

### 6.6.1 Dose Administration/Escalation

## **6.6.1.1** Dose Administration (Preparation)

Details on preparation and administration mRNA-5671/V941 and pembrolizumab are provided in the appropriate Pharmacy or Procedures Manual.

### **6.6.2** Definition of Dose-limiting Toxicity

All toxicities will be graded using NCI-CTCAE Version 4.0 based on the investigator assessment.

The DLT window of observation will be 21 days from the first dose of study treatment (Cycle 1). Participants will be monitored for DLTs during treatment with mRNA-5671/V941 as a monotherapy as well as in when mRNA-5671/V941 is administered in combination with pembrolizumab.

For dose-escalation decisions, an evaluable participant is defined as a participant who meets one of the following criteria:

• Receives any amount of an mRNA-5671/V941 dose alone or in combination with a pembrolizumab dose and experiences a DLT during Cycle 1.

24-MAR-2022

V941-001-08 FINAL PROTOCOL

Receives 100% of an mRNA-5671/V941 dose in Arm A, Cycle 1 or 100% of an mRNA-5671/V941 dose and/or ≥ 90 % of a pembrolizumab dose in Arm B, Cycle 1, is followed up for ≥ 21 days after the first dose of study treatment, and does not experience a DLT.

Participants who are not considered to be evaluable may be replaced (Section 5.5).

The occurrence of any of the following toxicities will be considered a DLT if judged by the investigator to be possibly related to administration of either mRNA-5671/V941 monotherapy or mRNA-5671/V941 in combination with pembrolizumab (ie, the toxicity is not attributable to the disease or disease-related processes under investigation or other causes):

- 1. Grade 4 nonhematologic toxicity (ie. Not a laboratory finding).
- 2. Grade 4 hematologic toxicity lasting  $\geq 7$  days, except thrombocytopenia:
- 3. Grade 4 thrombocytopenia of any duration
- 4. Grade 3 thrombocytopenia associated with clinically significant bleeding
- 5. Any nonhematologic AE ≥ Grade 3 in severity should be considered a DLT, with the following exceptions: Grade 3 fatigue lasting ≤ 3 days; Grade 3 diarrhea, nausea, or vomiting that does not require anti-emetics or anti-diarrheals per standard of care; Grade 3 rash that does not require corticosteroids or anti-inflammatory agents per standard of care.
- 6. Any Grade 3 or Grade 4 nonhematologic laboratory value that meets one of the following criteria:
  - Clinically significant medical intervention is required to treat the participant.
  - The abnormality leads to hospitalization.
  - The abnormality persists for >1 week.
  - The abnormality results in a drug-induced liver injury.

The following are exceptions: clinically nonsignificant, treatable, or reversible laboratory abnormalities, such as those related to liver function and uric acid.

7. Febrile neutropenia Grade 3 or Grade 4:

V941-001-08 FINAL PROTOCOL

• Grade 3 is defined as absolute neutrophil count (ANC) < 1000/mm3 with a single temperature of > 38.3°C (101°F) or a sustained temperature of ≥ 38°C (100.4°F) for more than 1 hour.

24-MAR-2022

- Grade 4 is defined as ANC < 1000/mm3 with a single temperature of > 38.3°C (101°F) or a sustained temperature of ≥ 38°C (100.4°F) for more than 1 hour with life-threatening consequences and urgent intervention indicated.
- 8. Prolonged delay (> 2 weeks) in initiating Cycle 2 due to treatment-related toxicity.
- 9. Any treatment-related toxicity that causes the participant to discontinue treatment during Cycle 1.
- 10. Grade 5 toxicity
- 11. Any other toxicity that is clinically significant and/or unacceptable and is judged to be a DLT by the investigator in collaboration with the Sponsor.

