When adding participants to a dose level in response to a "stay" decision, the number of additional participants to be enrolled is capped to minimize the exposure to a dose that may be unacceptably toxic (denoted as DU in Table 1). Secondly, to determine how many more participants can be enrolled at the dose level, one can count steps in diagonal direction (down and to the right) from the current cell to the first cell marked DU. For example, if 1 of 3 participants have experienced a DLT at a given dose level, no more than an additional 3 participants should be enrolled at this dose level until additional DLT data are available. This is because this dose level would be considered unacceptably toxic if all 3 of the additional participants experience a DLT (ie, 4/6 participants with DLT in Table 1). The same principles will be applied whether 3, 4, 5, or 6 participants are initially enrolled at that dose level.

A D or DU decision at the lowest dose level will stop the trial. An E decision at the highest dose level will result in staying at that level. During dose finding, it may be acceptable to deescalate to an intermediate dose that was not predefined and not previously-studied if evaluation of toxicity at such a dose is desired. If this approach is taken, 3 to 6 new

participants may be enrolled at the new intermediate dose, and the aforementioned rules should be used to determine further enrollment at this dose level.

After 14 participants have been enrolled at any of the tested doses (including intermediate doses), dose finding will stop if the mTPI table indicates "S" for staying at current dose. Otherwise, up to 14 new participants may be enrolled at a lower dose if "D" or "DU" is indicated, or at a higher dose if "E" is indicated.

The pool-adjacent-violators-algorithm [Ji, Y. 2013] will be used to estimate the DLT rates across doses. The dose with an estimated DLT rate closest to 30% will be treated as a preliminary MTD. However, the totality of the data will be considered before deciding on the dose(s) to carry forward to Part 2, and the escalation schedule may be adjusted based on pharmacodynamic, PK, and safety data emerging throughout the trial. The preliminary RP2D of mRNA-5671/V941 in the combination arm (Arm B) will not exceed, but may be equal to, the preliminary RP2D in the mRNA-5671/V941 monotherapy arm (Arm A).

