#### 5.5 **Participant Replacement Strategy**

In order to adequately evaluate the safety of the doses administered in this study, all participants enrolled must meet the criteria for evaluability for Cycle 1. Participants are considered nonevaluable and will be replaced if:

- They are allocated but not treated.
- They discontinue from the trial prior to completing all the safety evaluations for reasons other than treatment-related adverse events during Cycle 1 in the dose finding phase of the study (Part 1).
- They receive less than 100% of the total mRNA-5671/V941 or less than 90% of the total pembrolizumab infusion in Cycle 1 (eg, if the infusion had to be discontinued due to an infusion reaction) and did not experience a DLT.

Participants who are not evaluable will be replaced unless accrual to the cohort has stopped. Nonevaluable participants will not be counted toward the total number of participants in the cohort for DLT evaluation.

If a participant experiences a DLT in Cycle 1, trial treatment may be discontinued following discussion between the Sponsor and investigator. However, if the participant is deriving clinical benefit from the trial treatment, the participant may be allowed to continue after discussion between the Sponsor and the investigator.

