# **Dose Modification and Toxicity Management of Infusion Reactions Related to Pembrolizumab**

Pembrolizumab may cause severe or life-threatening infusion-reactions including severe hypersensitivity or anaphylaxis. Signs and symptoms usually develop during or shortly after drug infusion and generally resolve completely within 24 hours of completion of infusion. Dose modification and toxicity management guidelines on pembrolizumab associated infusion reaction are provided in Table 6.

Table 6 Guidelines for Pembrolizumab Infusion Reaction Dose Modification and Treatment

Treatment	Premedication at Subsequent Dosing
Increase monitoring of vital signs as medically indicated until the participant is deemed medically stable in the opinion of the investigator	None
Stop Infusion Additional appropriate medical therapy may include but is not limited to:  IV fluids Antihistamines NSAIDs Acetaminophen Narcotics Increase monitoring of vital signs as medically indicated until the participant is deemed medically stable in the opinion of the investigator.  If symptoms resolve within 1 hour of stopping drug infusion, the infusion may be restarted at 50% of the original infusion rate (eg, from 100 mL/hr to 50 mL/hr). Otherwise dosing will be held until symptoms resolve and the participant should be premedicated for the next scheduled dose.  Participants who develop Grade 2 toxicity despite adequate premedication should be permanently discontinued from further study	Participant may be premedicated 1.5 h (±30 minutes) prior to infusion of pembrolizumab with: Diphenhydramine 50 mg PO (or equivalent dose of antihistamine). Acetaminophen 500 to 1000 mg PO (or equivalent dose of analgesic).

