## 9.5 Analysis Populations

## 9.5.1 Safety Analysis Populations

The All-Subjects-as-Treated (AsaT) population will be used for the analysis of safety data in this study. The AsaT population consists of all participants who received at least 1 dose of study treatment.

The DLT evaluable population includes AsaT participants that meet the criteria for DLT evaluability (eg, finished Cycle 1 without a DLT or experienced a DLT in Cycle 1). See Section 6.6.2 for details.

At least 1 laboratory or vital sign measurement obtained subsequent to at least 1 dose of study treatment is required for inclusion in the analysis of each specific parameter. To assess change from baseline, a baseline measurement is also required.

Data from participants who crossover from monotherapy to the combination therapy will be presented separately.

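### Sections 5.5 and 6.6.2 can give different DLT-evaluable sets in Arm B, and the SAP points only to 6.6.2, so the primary DLT denominator is ambiguous

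*Combined protocol and SAP*

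**What the plan says.** Section 6.6.2 counts a participant as evaluable for dose decisions by either of two routes. The first is a DLT in Cycle 1 after any amount of vaccine. The second applies without a DLT. In Arm B it requires "100% of an mRNA-5671/V941 dose and/or ≥ 90 % of a pembrolizumab dose in Arm B, Cycle 1", and that the participant "is followed up for ≥ 21 days after the first dose of study treatment, and does not experience a DLT". The section adds that nonevaluable participants *may* be replaced, and cites Section 5.5 for that.

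Section 5.5 lists who is nonevaluable. One entry, limited to participants without a DLT, reads "They receive less than 100% of the total mRNA-5671/V941 or less than 90% of the total pembrolizumab infusion in Cycle 1", with the example "eg, if the infusion had to be discontinued due to an infusion reaction". It continues: "Nonevaluable participants will not be counted toward the total number of participants in the cohort for DLT evaluation". Here such participants *will* be replaced while the cohort is still accruing.

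SAP Section 9.5.1 says: "The DLT evaluable population includes AsaT participants that meet the criteria for DLT evaluability". It follows this with an illustrative gloss that has no dose threshold, and sends the reader to 6.6.2 for details. Section 9.4.2 makes DLT incidence the primary safety endpoint. Table 1 in Section 4.3.4 is indexed by the number evaluable for DLT. Section 9.6.1 reports the DLT rate at the RP2D with an 80% credible interval under a Beta(1,1) prior.

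**The concern.** The two sections use opposite connectives for the same two thresholds. Not being excluded under 5.5 requires both the full vaccine dose and at least 90% of pembrolizumab. Under 6.6.2, *and/or* allows either one to suffice. It can also be read as *and*, which would agree with 5.5, but the text does not say which reading applies, and no passage says which section prevails.

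The possible error has one direction. A participant with a DLT is evaluable under both sections, so the looser reading can add only DLT-free participants. After at least one DLT, it can lower the Arm B rate and never raise it, and it can make the mTPI decision less strict.

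**Working it through.** **1. The two rules side by side** (Arm B, no DLT, at least 21 days of follow-up)

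| Vaccine | Pembrolizumab | 6.6.2, *or* reading | 6.6.2, *and* reading | 5.5 |
|---|---|---|---|---|
| 100% | ≥90% | evaluable | evaluable | evaluable |
| 100% | <90% | evaluable | not | not |
| <100% | ≥90% | evaluable | not | not |
| <100% | <90% | not | not | not |

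Under the *or* reading, the sections disagree in two of four rows.

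**2. Can a discordant case arise?** Section 6.1.2 gives pembrolizumab 30 to 60 minutes after the vaccine, so row 2 is the natural case. For a Grade 2 infusion reaction, Table 6 stops the infusion and allows a restart if symptoms resolve within an hour. If they do not: "Otherwise dosing will be held until symptoms resolve and the participant should be premedicated for the next scheduled dose". That can leave less than 90% given. The event is below Grade 3 (DLT item 5) and need not end treatment (DLT item 9).

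**3. Reproducing Table 1.** Inputs from Section 4.3.4: target 0.30, ε1 = ε2 = 0.03, Beta(1,1) prior. With x DLTs in n, the posterior is Beta(1+x, 1+n−x). Compute the unit probability mass (posterior probability divided by interval width) on (0, 0.27), (0.27, 0.33) and (0.33, 1). The largest gives E, S or D respectively. DU applies if P(p > 0.30) exceeds a cutoff.

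The plan does not state the cutoff. Its worked examples bracket it:
- 2/3 is D, with P(p > 0.30) = 0.916.
- 4/6 is DU, with P(p > 0.30) = 0.971.

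I assume 0.95. That reproduces the worked examples (0/3 E, 1/3 S, 2/3 D, 3/3 DU, 4/6 DU) and the legible rows 0 to 3 of Table 1. The lower rows are scrambled in the text available and could not be checked cell by cell.

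**4. Adding one DLT-free participant.** The documents do not give the number of partly dosed participants; one is assumed, before any replacement data. For example:
- 2/3: unit masses E 0.23, S 0.76, D 1.33, so D.
- 2/4: unit masses E 0.47, S 1.32, D 1.19, so S.

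Over n = 3 to 14, 12 cells change:

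| Change | Cells |
|---|---|
| D to S | 2/3→2/4, 3/5→3/6, 4/8→4/9, 5/10→5/11, 6/12→6/13 |
| DU to D | 3/4→3/5, 4/6→4/7, 5/9→5/10, 6/11→6/12, 7/13→7/14 |
| S to E | 1/5→1/6, 2/10→2/11 |

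The five changes ending in S run from D or DU to S at any cutoff in the bracket. The DU-to-D changes depend on the cutoff. The S-to-E changes matter only below the top dose level, because "An E decision at the highest dose level will result in staying at that level". With no DLTs the decision is E at every n from 3 to 14.

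**5. Effect on the estimate** (80% credible interval: 10th and 90th percentiles of the posterior)

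| Result | Observed rate | 80% interval |
|---|---|---|
| 4/13 | 30.8% | 18.5 to 49.2% |
| 4/14 | 28.6% | 17.2 to 46.4% |
| 0/13 | 0% | upper limit 15.2% |
| 0/14 | 0% | upper limit 14.2% |

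**The case against.** The strongest reply is that this is loose drafting rather than a contradiction. Section 5.5 is explicit about the disputed case, and only the *and* reading of 6.6.2 is compatible with it. The *or* reading would also count a participant with an incomplete vaccine dose in a vaccine dose-finding study, which is implausible. Section 6.6.2 does cite 5.5. This makes *and* the more likely intention, but it does not settle the definition: the citation concerns replacement only, and a reader who follows the SAP lands on the ambiguous sentence.

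The affected group is narrow. Arm A and participants with a DLT are untouched. Related Grade 3 or 4 infusion reactions would generally be DLTs, a Grade 2 reaction that resolves within an hour may be restarted, and a late stop could still meet 90%. All of this stands. It makes the case uncommon without removing it, and 5.5 itself names it.

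Replacement can restore n. If the replacement has no DLT, the count and the decision end up the same. The cell changes therefore apply to a decision taken before replacement or after accrual stops.

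The decision effect is also less than 12 cells suggests. Two changes do nothing at the top dose, and five de-escalate either way and rest on the assumed cutoff (7/14 gives 0.949987, barely under 0.95). The five D-to-S changes start from observed rates of 50 to 67%. If the true DLT rate were 5 to 10% (an assumption), 2/3 would have probability 3p²(1−p) = 0.7 to 2.7%. Section 4.3.2 reports no DLTs with the related vaccine. These points limit the likely size. They do not supply a definition.

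**Conclusion.** The concern holds and should be fixed. The plan does not uniquely define the Arm B DLT-evaluable set, and the SAP's single reference leads to the ambiguous wording. If the looser reading is used, the error runs only toward a lower DLT rate and a less strict decision.

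The exposure is mainly in small cohorts: 2/3 = 66.7% (D) against 2/4 = 50.0% (S). The effect on a final estimate near 14 participants is about two percentage points (30.8% against 28.6%). With no DLTs, only the credible interval changes, with its upper limit moving by about one point.

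These sizes assume one partly dosed, DLT-free participant who has not been replaced. The count of 12 cells also assumes the 0.95 cutoff. Confidence is high that the wording is inconsistent; how many participants it touched cannot be known from the documents. The difference between *may* and *will* be replaced is secondary: the two can be read together.

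**What to change.** Reconcile Sections 5.5, 6.6.2 and 9.5.1 into one DLT-evaluable definition for analysis. For DLT-free Arm B participants, put *and* in place of *and/or* in 6.6.2 so that it matches the exclusion already stated in 5.5. Use the 5.5 replacement wording in both places, and have 9.5.1 refer to the reconciled definition. This concerns the analysis population only and changes no dosing or management rule.

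Amendment 8 prepares for close-out of the study, so Part 1 may already be complete. In that case, state in the report which rule was applied, and give the Arm B DLT rate and 80% credible interval under both readings.

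The cost is a few words in 6.6.2 and 9.5.1 and possibly one or two replacement participants, which 5.5 already provides for. If Part 1 is complete, it is one extra line in the DLT table.

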AST / ALT Elevation or Increased Bilirubin	Grade 2	Withhold	Administer corticosteroids (initial dose of 0.5-1 mg/kg prednisone or equivalent) followed by taper	Monitor with liver function tests (consider weekly or more frequently until liver enzyme value returned to baseline or is stable)
	Grade 3 or 4	Permanently discontinue	Administer corticosteroids (initial dose of 1-2 mg/kg prednisone or equivalent) followed by taper	
T1DM or Hyperglycemia	New onset T1DM or Grade 3 or 4 hyperglycemia associated with evidence of β- cell failure	Withhold a	Initiate insulin replacement therapy for participants with T1DM     Administer antihyperglycemic in participants with hyperglycemia	Monitor participants for hyperglycemia or other signs and symptoms of diabetes
Hypophysitis	Grade 2	Withhold	Administer corticosteroids and initiate hormonal replacements as clinically	Monitor for signs and symptoms of hypophysitis (including hypopituitarism and adrenal insufficiency)
	Grade 3 or 4	Withhold or permanently discontinue a	indicated	

C Confidential

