#### PRODUCT: V941

### PROTOCOL/AMENDMENT NO.: 001-08

irAEs	Toxicity Grade (CTCAEv4.0)	Action With Pembrolizumab Monotherapy, Coformulations or IO Combinations	Corticosteroid and/or Other Therapies	Monitoring and Follow-up
Hyperthyroidism	Grade 2	Continue	Treat with non-selective beta- blockers (eg, propranolol) or thionamides as appropriate	Monitor for signs and symptoms of thyroid disorders
	Grade 3 or 4	Withhold or	tinonamides as appropriate	
		Permanently discontinue a		
Hypothyroidism	Grade 2-4	Continue	Initiate thyroid replacement hormones (eg, levothyroxine or liothyronine) per standard of care	Monitor for signs and symptoms of thyroid disorders
Nephritis and renal dysfunction	Grade 2	Withhold	Administer corticosteroids (prednisone 1-2 mg/kg or	Monitor changes of renal function
renar dystanetron	Grade 3 or 4	Permanently discontinue	equivalent) followed by taper	
Myocarditis	Grade 1	Withhold	Based on severity of AE administer corticosteroids	Ensure adequate evaluation to confirm etiology and/or exclude other causes
	Grade 2, 3 or 4	Permanently discontinue		

irAEs	Toxicity Grade (CTCAEv4.0)	Action With Pembrolizumab Monotherapy, Coformulations or IO Combinations	Corticosteroid and/or Other Therapies	Monitoring and Follow-up
All Other irAEs	Persistent Grade 2	Withhold	Based on severity of AE administer corticosteroids	Ensure adequate evaluation to confirm etiology or exclude other causes
	Grade 3	Withhold or discontinue b		
	Recurrent Grade 3 or Grade 4	Permanently discontinue		

AE(s)=adverse event(s); ALT= alanine aminotransferase; AST=aspartate aminotransferase; CTCAE=Common Terminology Criteria for Adverse Events; DRESS=Drug Rash with Eosinophilia and Systemic Symptom; GI=gastrointestinal; IO=immuno-oncology; ir=immune related; IV=intravenous; SJS=Stevens-Johnson Syndrome; T1DM=type 1 diabetes mellitus; TEN=Toxic Epidermal Necrolysis; ULN=upper limit of normal.

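### The exception after DLT criterion 6 is too broad: exempting laboratory values that are merely treatable or reversible cancels the criterion's own conditions and leaves a narrow gap in DLT counting

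*Combined protocol and SAP*

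**What the plan says.** Section 6.6.2 lists eleven criteria. Meeting any one makes a possibly related toxicity a DLT.

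Criterion 6 covers Grade 3 or 4 nonhematologic laboratory values that meet at least one of four conditions:
- "Clinically significant medical intervention is required to treat the participant"
- the value leads to hospitalization
- "The abnormality persists for >1 week"
- "The abnormality results in a drug-induced liver injury"

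The next sentence reads: "The following are exceptions: clinically nonsignificant, treatable, or reversible laboratory abnormalities, such as those related to liver function and uric acid". The three descriptions are separate alternatives joined by *or*.

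Criterion 5 reads "Any nonhematologic AE ≥ Grade 3 in severity should be considered a DLT, with the following exceptions". The exceptions that follow concern fatigue, gastrointestinal symptoms and rash, and do not mention laboratory values. Criterion 1 excludes laboratory findings. Criterion 8 counts a delay of more than two weeks to Cycle 2, criterion 9 counts "Any treatment-related toxicity that causes the participant to discontinue treatment during Cycle 1", and criterion 11 is a catch-all left to the investigator with the Sponsor.

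Section 9.4.2 names DLT incidence as the primary safety endpoint. The count feeds the mTPI decisions (Section 4.3.4, Table 1), the DLT rate at the RP2D with its 80% credible interval (Section 9.6.1) and the pause rule at more than 33% (Section 4.4.1).

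**The concern.** Most Grade 3 or 4 laboratory abnormalities are treatable, reversible or both. Read as written, the exception can therefore remove the events that the four conditions were meant to capture. An investigator who follows the literal text will not count a Grade 3 electrolyte value that needed intravenous correction and recovered. One who follows the evident purpose of criterion 6 will count it. The literal reading can only lower the DLT count, so any error favors keeping the dose and reporting a lower DLT rate.

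**Working it through.** **Step 1. What the exception can act on.** A value that meets none of the four conditions is not a DLT under criterion 6 anyway. The exception therefore matters only for a value that meets one.

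| Condition in criterion 6 | Wording in the exception that can cancel it |
|---|---|
| Clinically significant intervention | *treatable* |
| Hospitalization | *reversible* or *treatable* |
| Lasts more than one week | *reversible* (a value can last over a week and still recover) |
| DILI | liver function is a named example |

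The term *clinically nonsignificant* does little harm. It cannot sensibly apply to a value that needed clinically significant intervention, and it has a natural use for a trivial value that lasts over a week.

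**Step 2. What other rules still catch.**
- *Criterion 5.* Sections 10.3.1 and 10.3.4 allow an abnormal laboratory finding to be an AE and ask for the diagnosis to be recorded where there is one. A hospitalized or DILI case will often be a Grade 3 or higher diagnosis and count under criterion 1 or 5. Whether criterion 5 reaches an isolated laboratory value is not stated.
- *Table 5 with criterion 9.* The rows "AST / ALT Elevation or Increased Bilirubin" and "Nephritis and renal dysfunction" require permanent discontinuation at Grade 3 or 4. Section 6.6.3 applies Table 5 to immune-related events from the vaccine. Discontinuation in Cycle 1 is a DLT. Events not judged immune-related are left to clinical practice.
- *Section 7.1.* Unacceptable adverse experiences require discontinuation, immune-related or not.
- *Section 8.3.4.1 with criterion 8.* Laboratory results must be acceptable before each dose, and a delay of more than two weeks counts.
- *Criterion 11.* Available, but discretionary.

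The gap is a Grade 3 or 4 laboratory event that was treated or prolonged, did not lead to discontinuation or a delay of more than two weeks, was acceptable for redosing, and was not counted under criterion 5 or 11.

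**Step 3. Reproduce the dose-finding table.** Inputs from Section 4.3.4 and Table 1: prior Beta(1,1), target 0.30, ε1 = ε2 = 0.03. For x DLTs in n participants the posterior is Beta(1+x, 1+n−x). The decision is the interval with the largest probability per unit length among (0, 0.27), (0.27, 0.33) and (0.33, 1). DU applies if P(p > 0.30) > 0.95; that cutoff is my assumption, as the documents do not state it. Results: 0/3 = E, 1/3 = S, 2/3 = D, 3/3 = DU and 4/6 = DU, which match the worked examples in Section 4.3.4.

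**Step 4. Effect of one exempted event.** 2/3 becomes 1/3, so D becomes S. 4/6 becomes 3/6, so DU becomes S. 7/14 becomes 6/14, so D becomes S.

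**Step 5. Chance of staying at 1.0 mg.** This is the highest planned level, and an E there means stay. The highest count that still reads E or S is 1 at n=3, 3 at n=6, 3 at n=8 and 6 at n=14. With true DLT rate p and exempted share r, P(stay) = P(X ≤ that count), X ~ Bin(n, p(1−r)), at one look. Example with n=3, p=0.30:
- r=0: 0.7³ + 3×0.3×0.7² = 0.343 + 0.441 = 0.784
- r=0.30, so the rate is 0.21: 0.79³ + 3×0.21×0.79² = 0.493 + 0.393 = 0.886

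Largest shift over n = 3 to 14:

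| True DLT rate | n | None exempted | 5% exempted | 30% exempted | Rise, points |
|---|---|---|---|---|---|
| 10% | 3 | 0.972 | 0.975 | 0.986 | 0.3 to 1.4 |
| 20% | 3 | 0.896 | 0.905 | 0.947 | 0.9 to 5.1 |
| 30% | 8 | 0.806 | 0.832 | 0.934 | 2.6 to 12.8 |

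**Step 6. Effect on the reported rate.** With the Section 9.6.1 prior, one exempted event at n=14 turns 1/14 = 7.1% (80% credible interval 3.6% to 23.6%) into 0/14 = 0% (0.7% to 14.2%).

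**The case against.** A reader might infer that criterion 6 contradicts itself and that nothing says which part prevails. That goes too far. The sentence is introduced as an exception and directly follows the criterion, and an exception ordinarily prevails over its rule. The fair complaint is that it is too wide. One could also read *clinically nonsignificant* as governing all three terms, which would remove most of the problem, but the sentence does not say so.

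A reader might also infer that DLTs were materially undercounted or that the 1.0 mg dose was wrongly supported. The documents do not support this either. They give no frequency for such events. Section 4.3.2 reports no DLTs in 75 patients on the similarly formulated product, and Section 9.9 expects a tolerable profile. The 12.8-point figure needs both a 30% exempted share, which is high given the other safeguards, and a true rate at the 30% target. It also describes one look, not the full sequential design.

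The strongest counterargument is criterion 5. If laboratory findings count as AEs there, as Section 10.3.1 suggests, the exception in criterion 6 has almost no effect. Against that, criterion 1 excludes laboratory findings, and criterion 6 would then be largely redundant. The point narrows the gap without closing it. It is also true that every DLT already rests on investigator grading and attribution, that exempted events still appear in the AE tables, and that dose selection uses the totality of the data.

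**Conclusion.** The exception is overbroad. Followed literally, it can remove from the primary safety endpoint events that criterion 6 was written to count. Other rules confine this to a narrow set, and the practical effect is probably small: at most 1.4 points on the chance of staying at 1.0 mg at a true DLT rate of 10%, and at most 5.1 points at 20%, even with 30% of DLTs exempted. These sizes rest on an assumed exempted share of 5% to 30%, a DU cutoff of 0.95 and a single look. A single event can still change a decision in a small cohort or turn a reported 1/14 into 0/14, so the wording is worth correcting. This is a point to consider, not a flaw that undermines the dose finding.

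**What to change.** In Section 6.6.2, delete *treatable* and *reversible* so that only clinically nonsignificant laboratory abnormalities are exempt. State that a value that required clinically significant intervention, led to hospitalization or resulted in DILI is always a DLT, and that the exception can apply only to the condition of lasting more than one week. In the DLT listing, flag any event already exempted under the present wording. A clause saying whether criterion 5 covers isolated laboratory values would settle the remaining doubt.

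The cost is a short text edit and one listing flag. The downside is a possibly slightly higher DLT count. Sample size is unaffected, and dosing decisions already made in Part 1 do not change. The gain is a DLT rate whose counting rule a reader can follow.
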